4. STUDY DESIGN

4.1. Study Design Overview

This Phase 1, open-label, multicenter, 2-arm study will be conducting using the mTPI dose-finding design ([Ji et al 2013](#)). Cohorts of patients will be enrolled to receive escalating doses of SYNB1891 administered by i.t. injection until the target DLT range (approximately 30%) for SYNB1891 monotherapy is determined based on DLTs observed in Cycle 1 (Arm 1). The dose selected as achieving the target DLT range will be considered the MTD. After all patients in Arm 1 Cohort 4 have completed their Cycle 1 DLT safety evaluation, Arm 2 will enroll its first cohort starting at the Arm 1 Cohort 3 dose level, with SYNB1891 administered by i.t. injection in combination with atezolizumab administered as an intravenous (IV) infusion at a dose of 1200 mg every 3 weeks (Q3W) until the RP2D for the combination regimen is determined (see [Figure 4](#)).

The mTPI algorithm (as further discussed in Section [4.2.3](#)) will be implemented separately in each arm.

Eligible patients will be enrolled sequentially and will receive the first dose of study treatment within 28 days of screening.

Safety will be monitored continuously by documentation of AEs, SAEs, clinical laboratory measurements, vital signs, and physical examinations. DLTs, as defined in Section [4.2.4](#), will be evaluated through the end of the first cycle.

Disease status will be assessed by the local Investigator using appropriate imaging every 2 cycles for the duration of study treatment administration to evaluate the SYNB1891-injected lesion(s) and an overall response of up to 5 noninjected target lesions in accordance with RECIST 1.1 ([Eisenhauer et al 2009](#) and [Appendix 1](#)), iRECIST ([Seymour et al 2017](#) and [Appendix 2](#)), and/or LYRIC ([Cheson et al 2016](#) and [Appendix 3](#)).

Tumor biopsies and blood samples will be collected at baseline and at prespecified time points on study to evaluate the pharmacokinetics (PK), as measured by qPCR bacterial kinetics, and PD effects of study treatment.

Figure 4: SYNB1891-CP-001 Study Design

[figure not shown]
Arm 1: SYNB1891 monotherapy:

- Safety and tolerability to determine single agent MTD
- Proof of mechanism by exploratory pharmacodynamic (PD) biomarkers
- mTPI dose escalation; enroll up to 28 patients

Arm 2: SYNB1891 combination with CPI:

- Safety and tolerability
- Proof of mechanism by exploratory biomarkers
- Enroll up to 20 patients, with potential to enroll up to 20 in extension

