4.2. Study Dosing Regimens

4.2.1. Treatments Administered

Patients enrolled to Arm 1 may receive up to four 21-day cycles of SYNB1891 monotherapy. On Days 1, 8, and 15 of Cycle 1 and Day 1 of Cycles 2 through 4, patients will receive an i.t. injection of SYNB1891 into an eligible lesion. If the initial eligible lesion undergoes complete regression and is no longer injectable (at the discretion of the Investigator), a subsequent eligible lesion (until no more eligible lesions remain) may be injected.

At the end of Cycle 4, patients in Arm 1 who do not have progressive disease (i.e., those who achieve and sustain complete response [CR], partial response [PR], or stable disease [SD]) may receive additional cycles of SYNB1891 administered by i.t. injection on Day 1 of each cycle for up to 24 months (i.e., Cycles 5 to 35) after the initial dose of study treatment until documentation of progressive disease or other discontinuation criteria, satisfaction of a predefined study stopping rule, or no eligible lesions remain.

Patients enrolled to Arm 2 may receive up to four 21-day cycles with SYNB1891 administered by i.t. injection into an eligible lesion on Days 1, 8, and 15 of Cycle 1 and Day 1 of Cycles 2 through 4. In addition, atezolizumab will be administered in accordance with its recommended dose and schedule (1200 mg IV Q3W) on Day 1 of each of the 4 planned cycles. On days when atezolizumab and SYNB1891 are both administered, SYNB1891 will be administered first, followed by at least 1 hour of observation prior to the atezolizumab infusion. Patients in Arm 2 who do not have progressive disease (i.e., those who achieve and sustain CR, PR, or SD) at the end of Cycle 4 on combination therapy may receive additional cycles of SYNB1891 and atezolizumab for up to 24 months (i.e., Cycles 5 to 35) after the initial dose of study treatment until documentation of progressive disease or other discontinuation criteria, satisfaction of a predefined study stopping rule, or no eligible lesions remain.

Locating and/or injecting the lesion may be performed using guided imaging at the discretion of the Investigator.

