- Review of the safety data for the first patient in a cohort (Sentinel patient) must be completed on or after Day 7 before the remaining 2 patients (non-Sentinel) in that cohort may be dosed (these 2 patients may be dosed concurrently). Observation of DLT(s) in a Sentinel patient will not necessarily preclude enrollment of subsequent

patients at the same dose level; rather, DLTs occurring in Sentinel patients will be reviewed individually by the SRC (consisting of the Sponsor Medical Monitor, the CRO Medical Monitor, all active Investigators, and other study personnel as needed) to determine appropriate dosing for subsequent patients.

- After all patients in a cohort have been assessed for DLTs (i.e., after each patient either experiences a DLT or completes the end of Cycle 1 safety assessment, whichever occurs first), the SRC will review all available safety data from the cohort and determine whether to escalate to the next higher SYNB1891 dose, enroll additional patients at the current dose, de-escalate to the next lower dose, or declare that the study objectives or stopping rules have been met. The decision will be informed by the mTPI algorithm recommendation to achieve the targeted toxicity interval.
- Patients must either experience a DLT during Cycle 1 or receive at least 2 of the 3 planned SYNB1891 injections to be considered evaluable for DLT evaluations and contribute to dose-escalation decisions for a given cohort. Patients who withdraw from the study for any reason other than DLTs prior to receiving the second injection of SYNB1891 in Cycle 1 may be replaced.

Once the RP2D of Arm 2 is determined, up to 20 additional patients may be enrolled in the RP2D cohort to fully characterize the safety profile of SYNB1891 in combination with atezolizumab.

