4.3.1. Dosing Delays and Interruptions

Study treatment dosing delays will be permitted in any treatment cycle if unforeseen circumstances prevent the patient from returning to the clinic on the scheduled day(s). A maximum delay of 2 days in Cycle 1 will be permitted. If administration of study treatment is delayed by > 2 days in Cycle 1, that dose is considered missed and the patient should receive the next dose at the next visit.

If a patient misses ≥ 2 SYNB1891 doses in Cycle 1, then the patient will be discontinued permanently from treatment and may be replaced (see Section 8.2.1). In Cycle 2 and beyond, if a patient misses the dose of SYNB1891, then the patient may be discontinued permanently from treatment, unless the Investigator's assessment of the benefit/risk suggests otherwise (after consultation with Sponsor). If treatment is permanently discontinued, patients will continue to be followed for safety as indicated for end of treatment and follow-up.

SYNB1891 treatment interruption can occur due to treatment-related toxicity, including Grade 3 or higher infections or local inflammation requiring antibiotics, and the start of a new cycle may not occur until the following criteria have been met:

- Nonhematologic toxicities have returned to either baseline or Grade ≤ 1 , or at the Investigator's discretion, Grade ≤ 2 if not considered a safety risk. This condition must be met within 14 days of the initial treatment interruption.
- Hematologic toxicities: ANC $\geq 1000/\text{mm}^3$ or have returned to baseline levels; platelet count $\geq 50,000/\text{mm}^3$ or has returned to baseline levels. This condition must be met within 14 days of the initial treatment interruption.
- If a patient requires treatment with a systemic antibiotic on study, SYNB1891 should be held for the duration of the antibiotic regimen and for 5 half-lives after the last dose of antibiotics. Once the patient is apyretic after completion of the antibiotic washout period, SYNB1891 may resume.

If the patient cannot meet the above conditions within the specified time frame, then study treatment should be permanently discontinued, unless the Investigator's assessment of the benefit/risk suggests otherwise (after consultation with Sponsor). The patient may be replaced (see Section 8.2.1).

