8.2.1. Patient Replacement

Patients who terminate participation in the study for any reason other than DLTs prior to receiving the second injection of SYNB1891 in Cycle 1 will be considered ineligible for the safety assessment required for dose-escalation decisions and may be replaced.

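### The DLT-evaluability rule counts injections but not follow-up, so a patient lost soon after the second injection enters the dose decision as a full non-DLT

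*Protocol*

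**What the plan says.** Protocol 4.2.3 makes a patient evaluable in one of two ways: a DLT during Cycle 1, or enough exposure, meaning that the patient must "receive at least 2 of the 3 planned SYNB1891 injections to be considered evaluable for DLT evaluations". The same bullet says that patients who withdraw for a reason other than a DLT "prior to receiving the second injection of SYNB1891 in Cycle 1 may be replaced". Section 8.2.1 uses the same cut-off: such patients leaving "prior to receiving the second injection of SYNB1891 in Cycle 1 will be considered ineligible for the safety assessment required for dose-escalation decisions". Section 4.3.1 adds a route for two or more missed "SYNB1891 doses in Cycle 1, then the patient will be discontinued permanently from treatment and may be replaced", but a patient who misses only the Day 15 injection does not reach it.

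The observation window is longer than this exposure rule implies. Section 4.2.1 says "Patients enrolled to Arm 1 may receive up to four 21-day cycles of SYNB1891 monotherapy", with Cycle 1 injections on Days 1, 8 and 15. Section 4.1 says that DLTs "will be evaluated through the end of the first cycle". The bullet before the evaluability rule in 4.2.3 has the Safety Review Committee (SRC) review a cohort once each patient has a DLT or "completes the end of Cycle 1 safety assessment, whichever occurs first".

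SAP VIII.B repeats the 2-of-3 count for dose-escalation decisions without a follow-up condition, and it omits the protocol's alternative of having had a DLT. SAP V.C rules out imputation for the primary objective.

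**The concern.** The exposure condition can be met on Day 8, while the DLT window runs to Day 21. A patient without a DLT who disappears from observation between those days satisfies the stated rule and is entered in Table 1 as one full non-DLT. No text removes this patient from the denominator or says what to do about the unobserved days. The SRC bullet assumes that such a patient does not exist: the patient neither has a DLT nor completes the assessment.

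The error runs in one direction. An unobserved DLT can only be missed, so the DLT percentage (the primary endpoint) is pulled down and the algorithm is pushed toward the next dose, about 3-fold higher. It matters most in cohorts of three, where a single patient separates escalate from stay. The same counts feed the pooled estimate used to name the preliminary MTD.

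Some DLT definitions in 4.2.4 also need time. Grade 4 hematologic toxicity must last at least 7 days, and one laboratory criterion needs persistence beyond a week. If such toxicity starts after a Day 8 injection, it cannot qualify under those criteria by Day 9.

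**Working it through.** **Share of the window unobserved.** Inputs: a 21-day cycle, the second injection planned for Day 8 (4.2.1), and a delay of at most 2 days in Cycle 1 (4.3.1). Counting the exit day as observed, the share is (21 − exit day)/21.

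- Exit on Day 8: 13/21 = 61.9%
- Exit on Day 9: 12/21 = 57.1%
- Exit on Day 10: 11/21 = 52.4%
- If Day 8 is missed and the second injection is the Day 15 dose: 6/21 = 28.6%

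The share therefore exceeds half only when the second injection received is the Day 8 dose.

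**Table 1, three-patient column.** Inputs: target 30%, Beta(1,1) prior, both epsilons 0.03. The posterior is Beta(1+x, 4−x) after x DLTs in 3. The unit probability mass is the posterior probability of each interval divided by its length, for (0, 0.27), (0.27, 0.33) and (0.33, 1).

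- 0/3: 2.65, 1.37, 0.30, so escalate
- 1/3: 1.10, 1.76, 0.89, so stay
- 2/3: 0.23, 0.76, 1.33, so de-escalate
- 3/3: 0.02, 0.11, 1.47, with P(rate > 30%) = 0.992, so unacceptably toxic (the 0.95 cut-off is assumed; the documents do not state one)

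All four decisions match the plan. The chance of escalating on the first three patients is therefore P(0/3).

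**Effect when a patient is lost.** The documents give no DLT timing and no loss rate, so both are assumed here: uniform onset over 21 days and exit on Day 9. A lost patient shows a DLT with probability p × 9/21. With k of three patients lost, P(0/3) = (1−p)^(3−k) × (1 − 9p/21)^k.

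- p = 0.40, none lost: 0.6³ = 21.6%
- p = 0.40, one lost: 0.6² × 0.8286 = 29.8%
- p = 0.40, two lost: 0.6 × 0.8286² = 41.2%
- p = 0.50: 12.5%, 19.6% and 30.9% in the same order

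**Averaged over a loss rate f.** Each patient shows no DLT with probability 1 − p(1 − f × 12/21), and P(0/3) is its cube.

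- p = 0.40, f = 5%: 0.6114³ = 22.9%
- p = 0.40, f = 10%: 0.6229³ = 24.2%
- p = 0.50, f = 5% and 10%: 0.5143³ = 13.6% and 0.5286³ = 14.8%

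**Sensitivity to timing.** With exit on Day 8 and one patient lost, p = 0.40 gives 29.6% under a constant hazard and 30.5% under linear accrual. If instead 75% of DLTs begin by Day 9, one lost patient gives 0.36 × (1 − 0.4 × 0.75) = 25.2%.

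**With follow-up required.** A cohort at 0/3 with one patient lost becomes 0/2. That is below the minimum of 3 per dose in 4.2.3, so escalation waits for another evaluable patient.

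**The case against.** The best counter-reading is that two injections are a necessary condition and not a sufficient one, and that the SRC bullet supplies the follow-up requirement. Section 4.2.3 also speaks of patients not yet fully evaluable, which fits that intention. But the SRC bullet sets when the committee meets, not who counts. The evaluability sentence names no second condition, and the SAP rule that will be programmed has none. The intention may well be right; the text does not deliver it.

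Three further objections stand, and they limit the point.

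- A reader might infer that anyone who stops after the second injection goes unobserved for most of the window. Section 8.2 does not support that. Patients who withdraw after a first dose must still complete the EOT and Safety Follow-up visits unless they withdraw consent for follow-up. Safety Follow-up at 30 ± 5 days after a Day 8 dose falls on Day 33 to 43, and adverse events are recorded through it. The EOT visit can fall anywhere within 14 days of the last dose, so laboratory data late in Cycle 1 may still be thin, but these patients are largely observed.
- Exits that would bias the rate most are largely DLTs already. Under 4.2.4, discontinuation by the Investigator for treatment-related toxicity in Cycle 1 is one. So is missing more than 33% of doses because of Grade 3 drug-related events, and one dose of three is 33.3%.
- A reader might infer that 8.2.1 forbids later replacement. It is silent after the second injection. The SRC may also enroll more patients at the same dose and is only informed by the algorithm. Nothing obliges it to do so for this patient.

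**Conclusion.** The gap is real and narrow. As written, a DLT-free patient who dies of disease, is lost, or withdraws follow-up consent shortly after the Day 8 injection counts as a full non-DLT with 52% to 62% of the window unseen, and no replacement is provided for. The bias is always toward escalation.

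Its size depends on assumptions that the documents do not settle. With uniform onset, exit on Day 9 and a true rate of 40%, a cohort that actually loses one of three patients has a 29.8% chance of 0/3 against 21.6%. Averaged over a 5% to 10% loss rate, the chance is about 23% to 24%. A reader might take the 29.8% or 41.2% figure as the expected distortion of the trial. It is not: those figures hold only when one or two of three patients are truly lost, and earlier DLT onset shrinks them. The two bullets in 4.2.3 and the SAP rule should be reconciled because the primary endpoint and every dose decision use this denominator and the correction is cheap.

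**What to change.** In Protocol 4.2.3, define a DLT-evaluable patient as one who has a DLT in Cycle 1, OR who receives at least 2 of the 3 injections AND has documented DLT safety follow-up through the end of Cycle 1 (Day 21). Accept that follow-up from the end-of-Cycle-1 assessment or from any EOT or Safety Follow-up contact covering the period, so that patients followed under 8.2 are not discarded. State in 4.2.3 and 8.2.1 that any other patient is non-evaluable for dose decisions and may be replaced. Carry the same definition into SAP VIII.B and restore the missing DLT alternative there; otherwise a patient with a DLT after one injection would not contribute to the escalation decision on the SAP's wording.

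The cost is a sentence in three places and an occasional replacement, with the time to enroll that patient and observe one 21-day cycle. Sections 5.1 and 10.6 already allow one replacement per cohort.

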4.2.3. Dose-finding with the mTPI Algorithm

In both study arms, each cohort will initially comprise 3 patients (a Sentinel patient and 2 non-Sentinel patients), with subsequent dose escalation governed by an mTPI design (Ji et al 2013).

The starting dose of SYNB1891 in the first cohort of Arm 1 will be 1×10^6 live cells and will be increased in approximately 3-fold increments in subsequent cohorts until MTD determination. If no MTD is identified, then the MTD will be considered the maximum dose at which a sufficient number of patients have been treated such that if 14 patients were administered that dose then either escalation or staying at the current dose would be recommended according to [Table 1](#). For example, if 8 patients were administered a dose level with 0 DLTs observed, even if all remaining 6 patients had a DLT, [Table 1](#) would indicate “stay at the current dose”; thus, the remaining 6 patients are not required to evaluate the MTD.

A mTPI design with a target DLT rate of approximately 30% will be applied for dose escalation and confirmation to determine the MTD/RP2D. In Arm 1, predetermined dose levels of 1×10^6 , 3×10^6 , 1×10^7 , 3×10^7 , 1×10^8 , 3×10^8 , and 1×10^9 live cells will be explored independently, with additional dose levels as necessary to determine the MTD. A de-escalation dose of 3×10^5 live cells is available if the starting dose is deemed not tolerable. All dose escalation and de-escalation decisions will be based on the occurrence of DLTs at a given dose during Cycle 1 and will be made jointly by the Investigators and the Sponsor.

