In [Table 1](#), the number of patients treated is indicated in the columns and the number of patients who experienced a DLT is indicated in the rows. Dosing decisions include escalate to the next higher dose (E), stay at the current dose (S), de-escalate to the next lower dose (D), and de-escalate to a lower dose and never test this dose again (i.e., unacceptably toxic dose; DU). During dose escalation, a minimum of 3 patients are required at each dose. Depending on accrual rate and occurrence of DLTs, 3, 4, 5 or 6 patients may be enrolled at each new dose until the last of those patients completes the Cycle 1 DLT assessment period. For example, the dose escalation rules will proceed as follows if 3 patients are enrolled: if 0 of the first 3 patients at a given dose level develops a DLT, then the dose can be escalated to the next level without further expansion. If 1 of the first 3 patients at a given dose level develops a DLT, no more than an additional 3 patients should be enrolled at this dose level until additional DLT data are available since this dose would be considered unacceptably toxic if all 3 of the additional patients experience a DLT (i.e., 4 of 6 patients). If 2 of the first 3 patients at a given dose level develop a DLT, the dose will be de-escalated to the next lower level. If 3 of the first 3 patients at a given dose level develop a DLT, this dose will be considered unacceptably toxic (i.e., the dose will be de-escalated and never re-escalated to that dose again). The same principle will be applied whether 3, 4, 5 or 6 patients are enrolled in the same dose cohort according to [Table 1](#).

Based on the mTPI design, the number of patients who are enrolled at a dose, but are not yet fully evaluable for DLT assessment, may not exceed the number of remaining patients who are at risk of developing a DLT before the dose would be considered unacceptably toxic (denoted as DU in [Table 1](#)). To determine how many more patients can be enrolled at a dose level, one can count steps in a diagonal direction (down and to the right) from the current cell to the first cell marked DU. In total, 3 to 14 patients may be enrolled at a given dose level.

Dose escalation and confirmation will end after 14 patients have been treated at any of the selected doses. The pool-adjacent-violators-algorithm (Ji et al 2013) will be used to estimate the

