4.5. Stopping Rules

The Sponsor may stop this study at any time. Investigators will be notified by the Sponsor or its designee if the study is stopped. The occurrence of the following events will require that further enrollment in the study be stopped:

- Grade 3 or higher systemic infection assessed as definitely related to SYNB1891.
- Death assessed as at least possibly related to study treatment.
- The Investigator, Medical Monitor(s), and/or Sponsor determines that an event or current data warrant stopping the study.

The SRC will review the data concerning these event(s), along with all other available data. Based on the results of their investigation, the SRC will determine appropriate follow-up and decide whether the study should be continued, amended or stopped.

If the study is stopped, the events will be investigated, and the study will be closed to further enrollment. Patients already participating in the study at the time the study is stopped will not receive further study treatment and the evaluations for the End-of-treatment (EOT)/Early Termination visit will be performed.

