9.7. Review of Safety Data

The Sponsor Medical Monitor in collaboration with the CRO Medical Monitor will be responsible for the ongoing review and evaluation of safety data, including AEs, clinical laboratory data, and any other safety evaluations, for the duration of the study.

The Sponsor will host Investigator teleconferences on a regular basis during the study. In addition, the Safety Review Committee (SRC; consisting of the Sponsor Medical Monitor, the CRO Medical Monitor, all active Investigators, and other study personnel as needed) will convene when all patients have completed the first cycle of study treatment in a given cohort and review all available safety information, including DLTs and all NCI CTCAE Grade 2 or higher toxicity data, as well as any other (e.g., PK/PD) data as indicated. Updated safety data on other ongoing patients, including data from later cycles, will be discussed as well.

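### The Arm 2 RP2D expansion of up to 20 patients has no cumulative DLT boundary and no timed look; extending Table 1 would be a cheap improvement

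*Protocol*

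**What the plan says.** **Expansion.** Protocol 4.2.3 allows that "up to 20 additional patients may be enrolled in the RP2D cohort to fully characterize the safety profile" of SYNB1891 with atezolizumab. Protocol 5.1 and 10.6 and SAP III.A and III.C repeat the number. None of them adds a stopping boundary, a batch size or a rule for revising the RP2D.

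**Dose-finding rule.** Table 1 covers 3 to 14 evaluable patients. The text says "In total, 3 to 14 patients may be enrolled at a given dose level". The number enrolled but not yet evaluable "may not exceed the number of remaining patients who are at risk of developing a DLT before the dose would be considered unacceptably toxic", counted along Table 1 to its DU cells, so this limit also ends at 14. Dose finding ends at 14 patients on a dose. An early exit is also described: "For example, if 8 patients were administered a dose level with 0 DLTs observed", six further DLTs would still read as stay, so the other six patients are not needed. That paragraph is written around Arm 1; reading it across to Arm 2 is an interpretation.

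**SRC review.** "After all patients in a cohort have been assessed for DLTs", the SRC decides whether to escalate, add patients, de-escalate or stop. "The decision will be informed by the mTPI algorithm recommendation to achieve the targeted toxicity interval". Section 9.7 likewise says the SRC "will convene when all patients have completed the first cycle of study treatment in a given cohort".

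**Other controls that reach the expansion.**
- Protocol 4.5 stops enrollment for one Grade 3 or higher systemic infection definitely related to SYNB1891 (which may be non-fatal), for one at least possibly related death, or when the Investigator, Medical Monitor or Sponsor "determines that an event or current data warrant stopping the study".
- Protocol 9.7 provides ongoing Medical Monitor review and regular Investigator teleconferences. Protocol 9.4 requires SAE reports within 24 hours.
- SAP V.D permits interim analyses, but both of those scheduled in SAP Appendix 5 fall in Arm 1.

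**The concern.** Small dose-finding cohorts are governed by a numeric toxicity rule, but the largest group planned at a single dose is not. The RP2D of the combination is part of the study's overall objective, and a full expansion would supply most of the patients at that dose. The DLT rate may still be poorly known when the expansion opens.

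A run of non-fatal DLTs in the expansion, for example repeated Grade 3 cytokine release syndrome (a DLT under item 3 of protocol 4.2.4), would trip neither event-based stopping rule. The SRC and the Sponsor have the power to act, but the plan gives them no preset count and no timed look. A dose well above the 30% target could therefore be fully enrolled unless someone uses discretion.

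**Working it through.** **1. Reproducing Table 1.** Inputs from its footnote: target 0.30, Beta(1,1) prior, both epsilons 0.03. With x DLTs in n patients the posterior is Beta(1+x, 1+n−x). E, S or D is the interval with the largest posterior mass per unit width among 0–0.27, 0.27–0.33 and 0.33–1. DU applies when Pr(p > 0.30) exceeds a cut-off, which neither document states.
- At cut-off 0.95, 76 of the 78 readable cells in rows 0–6 match. The exceptions are 5/9 (printed D; posterior 0.953, so computed DU) and 5/10 (printed S, computed D).
- At 0.955 or 0.96, 77 of 78 match (exception 5/10).
- Rows 7 and above are broken in the text available and were not scored. The exceptions may also come from text extraction.

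**2. Share of patients at the RP2D.** Entering from 14: 20/34 = 59%. The early exit needs x + (14 − n) ≤ 6, the highest S count at n = 14. With x = 0 the smallest n is 8, so the share is 20/28 = 71%.

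**3. Uncertainty when the expansion opens.** Under the plan's prior, Pr(true DLT rate > 40%) is 1% after 0/8, 22% after 4/14, 40% after 5/14 and 61% after 6/14. A dose at 6/14 would be chosen only if no tested dose had an estimate nearer 30%.

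**4. Extending the table.** Looks after 4, 8, 12 and 16 expansion patients, cumulative count at the dose, cut-off 0.95 (inferred). Pr(p > 0.30) is in brackets.
- Entry at n = 14: first DU counts 9/18 (0.967), 11/22 (0.979), 12/26 (0.964), 14/30 (0.976).
- Entry at 0/8: 8/16 (0.960), 10/20 (0.974), 11/24 (0.956). At n = 12 the boundary is 7, which four patients cannot reach.

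**5. Chance of crossing before patient 20.** Exact binomial recursion: after each patient the count rises by one with probability p, and paths at or above the boundary are removed at each look. There is no reporting lag. As a check, from 5/14 the first look needs 4 of 4, so at p = 0.40 its share is 0.4⁴ = 0.0256. From 6/14 it needs at least 3 of 4: 4 × 0.4³ × 0.6 + 0.4⁴ = 0.1792.

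| True DLT rate | from 0/8 | from 4/14 | from 5/14 | from 6/14 |
|---|---|---|---|---|
| 30% | 0.2% | 1% | 5% | 18% |
| 40% | 2% | 8% | 21% | 43% |
| 50% | 11% | 27% | 48% | 71% |
| 60% | 33% | 57% | 77% | 91% |

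The results are identical at 0.95 and 0.955. At 0.96 the columns from n = 14 are unchanged, but the 0/8 column falls to 0.04%, 0.6%, 4% and 18%.

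**6. Effect on enrollment.** The documents give no accrual rate. Assume 4 more patients enter while each look is being assessed, and that every crossing closes the dose.

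| True DLT rate | from 0/8 | from 4/14 | from 5/14 | from 6/14 |
|---|---|---|---|---|
| 40%: mean expansion size | 19.98 | 19.7 | 19.0 | 16.7 |
| 60%: mean expansion size | 19.6 | 17.8 | 15.4 | 12.0 |

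With a lag of 8 instead, the mean size is 19.6 from 4/14 at 60% and 19.65 from 5/14 at 40%.

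**The case against.** The strongest reply is that the expansion is already watched and that a formal boundary adds little.

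Much of this stands. A reader might infer that the expansion is unmonitored, and the documents do not support that. One definitely related Grade 3 or higher systemic infection stops enrollment, and this is a key hazard of a live bacterial product. Medical Monitors review data continuously, Investigators confer regularly and sit on the SRC, SAEs reach the Sponsor within 24 hours, and a discretionary stop is available at any time.

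A reader might also infer that the protocol fixes a single SRC review after all 20 patients. That follows only if the 20 are treated as one cohort, which the text does not say. Nor is the 3-to-14 limit a clear contradiction of the expansion: it sits in the dose-finding rules and can be read as confined to them, though the protocol does not say so.

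The enrollment figures are upper bounds. They assume that every pause becomes closure and that no existing control acts first. At 40% from 4/14 they spare about 0.3 of a patient (20 − 19.7). The large effects need a clearly toxic dose or a high entry count, and a longer lag erodes them. The cut-off is inferred, and the 0/8 results depend on it.

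What the reply does not remove is the gap itself. None of these controls says how many other non-fatal DLTs should prompt action, or when the SRC should count them.

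**Conclusion.** The point holds as a cheap improvement that should be made; it is not a contradiction or an absence of oversight. For up to 20 patients at the Arm 2 RP2D, neither document states a cumulative DLT boundary, a timed look or a rule for revising the RP2D.

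The benefit depends on where the expansion starts. It is material against clearly toxic doses: at a true rate of 60%, a crossing is likely from any of the three 14-patient entries examined. It is also material after a high entry count. It is slight from 0/8, or from 4/14 at 40%. A reader might infer that the rule would sharply cut exposure in the typical case; the calculation does not support that.

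The sizes rest on the inferred DU cut-off, looks every 4 patients, independent DLTs at a constant rate, and, for enrollment, a 4-patient lag with closure at every crossing. The absence of a stated rule rests on none of these assumptions.

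**What to change.** 1. Extend Table 1 to n = 34 with its stated target, prior and epsilons, and state the DU cut-off actually used. Have the SRC apply it to cumulative DLTs at the RP2D after about every 4 evaluable expansion patients, without holding enrollment between looks. A crossing triggers a pause and SRC review. This is deliberately softer than DU in dose finding, which bars the dose for good, so the text should say so.
2. State that the 3-to-14 limit covers dose finding only, and whether the pending-patient limit applies in the expansion.
3. State that the final RP2D uses all DLT-evaluable patients at that dose, including the expansion.

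**Cost.** A longer table and about four added SRC reviews; the end-of-cohort review is already required. If the true rate is 30%, an unneeded pause occurs in 1%, 5% or 18% of trials entering from 4/14, 5/14 or 6/14. Looks every 5 patients would save one review but raise these to 2%, 8% and 26% at cut-off 0.95 (2%, 7% and 20% at 0.955). Patients enrolled during the 21-day assessment lag would still be treated. Items 2 and 3 take a sentence or two each and are worth adding even if the Sponsor prefers another boundary.
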